5.1.2.8 Potential Risk due to Reduction of Target Protein HTT

By specifically targeting mRNA from both *HTT* alleles, RO7234292 lowers levels of both mHTT protein and normal wild-type huntingtin (wtHTT) protein in all patients, regardless of genetic variations. The ASO modality provides partial, transient, reversible, and titratable HTT lowering. Partial HTT lowering is safe and well tolerated in normal rodents and non-human primates, as shown in multiple studies using ASOs and non-reversible approaches. Furthermore, no safety signals of concern emerged during the completed Phase I/IIa study of RO7234292 in adults with HD (see RO7234292 Investigator's Brochure), in which partial lowering was achieved.

Transgenic mice expressing human mHTT develop progressive HD-like phenotypes that recapitulate many aspects of HD in humans. ASO-mediated mHTT lowering provides therapeutic benefits and often restores normal functioning in transgenic and fully humanized animal models of HD, with generally similar results regardless of whether wtHTT is also lowered. Moreover, no detrimental effects of partial wtHTT lowering in animal models have been reported in multiple studies using ASOs and non-reversible approaches.

Still, the current understanding of the diverse cellular functions of HTT suggests potential theoretical risks associated with reducing total HTT levels in people with HD. More than two decades of research findings implicate HTT in a wide array of cellular functions, including microtubule-based transport, F-actin-based trafficking, Rab-based trafficking, brain-derived neurotrophic factor transport, ciliogenesis, transcription, chromatin modification, post-transcriptional gene-expression regulation, neurogenesis, synaptogenesis, synaptic plasticity, signaling pathways, cell stress responses, cell survival, selective macro-autophagy and DNA damage repair, as detailed in a recent review article (Liu and Zeitlin 2017).

Although functional HTT (mutant or wild-type) is essential for embryogenesis, near-complete genetic ablation of HTT has little or no reported neurological effect in normal adult animals. However, complete ablation of wtHTT protein expression throughout life results in a worsening motor phenotype and, in male transgenic mice, age-dependent emergence of brain atrophy and decreased testicular size (Van Raamsdonk et al. 2005). In contrast, decreases in mHTT protein expression ameliorate disease, and increases in mHTT protein exacerbate disease in animal models of HD, regardless of concomitant changes in wtHTT protein levels.

No clinically significant new neurologic events were observed in the completed Phase I/IIa study. As a precaution, a full neurologic examination will be conducted at

each study visit (on dosing days before and after dosing), and additional monitoring of cognition will be conducted throughout the study using the MoCA.

5.1.3 Management of Patients Who Experience Adverse Events

5.1.3.1 Dose Modifications

No dose modifications are permitted in this study, whether by varying the amount of study drug volume injected or the frequency of procedure per protocol (i.e., all participants will receive 20 mL of blinded study drug per injection on a Q8W basis).

5.1.3.2 Treatment Interruption

Study drug may be temporarily suspended in patients who experience toxicity considered to be related to study drug. If study drug has been withheld for >60 days, from the date of the first missed dose, because of signs of persistent drug-induced toxicity or if the scheduled dose has been missed, the investigator should consult the Medical Monitor to determine if discontinuation from study drug is warranted. Study drug may be suspended for reasons other than toxicity (e.g., surgical procedures) with Medical Monitor approval. The investigator and the Medical Monitor will determine the acceptable length of treatment interruption.

5.1.3.3 Management Guidelines

Guidelines for management of specific adverse events are outlined in [Table 3](#).

Additional guidelines are provided in the subsections below.

Initial clinical laboratory tests with results meeting criteria for withholding study drug must be repeated on new specimens as soon as possible, and results must be available prior to administering the next dose of study drug. In general, patients who do not reach the stopping rule may continue dosing; however, the investigator and Sponsor should confer as to whether additional close monitoring of the patient is indicated.

Table 3 Guidelines for Management of Patients Who Experience Adverse Events

Event	Action to Be Taken
Elevations in CSF WBC count or proteins or suspected meningitis, radiculitis, arachnoiditis, hydrocephalus, or other acute neurologic symptoms	
 • Withhold study drug if diagnosis of meningitis, radiculitis, arachnoiditis, hydrocephalus, or acute neurologic symptoms is suspected and initiate appropriate diagnostic work-up as indicated. 
 • Clinical signs and symptoms of hydrocephalus (e.g., new onset of persistent or worsening gait disturbance, change in level of consciousness/cognition, changes in continence, or a combination of all three signs) are required for diagnosis of suspected hydrocephalus. • Clinical signs and symptoms of meningitis (e.g., headache, stiff neck, fever) plus confirmatory WBC count are required for diagnosis of suspected meningitis; and clinical signs and symptoms are required for diagnosis of radiculitis, arachnoiditis, or acute neurologic symptoms. Isolated low-level (e.g., 5–50/μL WBC count) elevations in CSF WBC count without clinical symptoms does not meet criteria for diagnosis of suspected meningitis. • The Medical Monitor should be consulted in all cases where CSF WBC count elevations above 10/μL are present, or a change from baseline in CSF proteins greater than twice baseline or where there is uncertainty to discuss next steps of patient management in the study. • If diagnosis of suspected meningitis, radiculitis, arachnoiditis, hydrocephalus, or other acute neurologic symptoms is refuted, the study drug may be resumed after consultation with the Medical Monitor. • In the event meningitis, radiculitis, arachnoiditis, hydrocephalus, or acute neurologic symptom diagnosis is confirmed, standard-of-care therapies should be instituted as indicated.

Table 3 Guidelines for Management of Patients Who Experience Adverse Events (cont.)

Thrombocytopenia	
 If platelet count is $\leq 100,000/\text{mm}^3$: 
 Monitor platelet count weekly If platelet count is $\leq 75,000/\text{mm}^3$ and $> 50,000/\text{mm}^3$ in the absence of major bleeding or clinically relevant non-major bleeding: 
 Withhold study drug until the platelet count has recovered to $> 100,000/\text{mm}^3$. The suitability of the patient for continued dosing and frequency of monitoring should be discussed with the Medical Monitor. If platelet count is $\leq 50,000/\text{mm}^3$: 
 Permanently discontinue study drug. Monitor platelet counts daily until two successive values show improvement. Then monitor every 2–3 days until platelet count is stable, and at least weekly until platelet count returns to normal. Treatment per standard of care should be considered for patients whose platelet count is $< 25,000/\text{mm}^3$.
Decreased renal function	
 Withhold study drug in the event of a persistent (> 2 weeks) decrease in eGFR or CrCl or increase in creatinine, as defined below: 
 eGFR or CrCl (using Cockcroft-Gault) $< 60 \text{ mL/min}$ Creatinine level increase of $2.0 \times$ above baseline Study drug may be resumed when follow-up test results show that the patient no longer meets the dose interruption criteria.
Elevated liver enzymes	
 ALT or AST is $> 3 \times \text{ULN}$: 
 Monitor weekly until ALT and AST return to $\leq 1.2 \times \text{ULN}$. Further investigation into the liver enzyme elevations may include hepatitis serologies and other diagnostic tests at the discretion of the investigator in consultation with the Medical Monitor. Withhold study drug in the event of liver enzymes that meet the following criteria without an alternative explanation (as discussed with the Medical Monitor): 
 ALT or AST $> 5 \times \text{ULN}$ ALT or AST $> 3 \times \text{ULN}$, combined with total bilirubin $> 2 \times \text{ULN}$ or INR > 1.5 ALT or AST $> 3 \times \text{ULN}$ coinciding with new appearance of fatigue, nausea, vomiting, right upper quadrant pain or tenderness, fever, rash, and/or concomitant eosinophilia. Discontinue study drug permanently if levels do not return to baseline after 30 days.

CrCl=creatinine clearance; CSF=cerebrospinal fluid; eGFR=estimated glomerular filtration rate; ULN=upper limit of normal.

5.2 SAFETY PARAMETERS AND DEFINITIONS

Safety assessments will consist of monitoring and recording adverse events, including serious adverse events and adverse events of special interest, performing protocol-specified safety laboratory assessments, measuring protocol-specified vital signs, and conducting other protocol-specified tests that are deemed critical to the safety evaluation of the study.

Certain types of events require immediate reporting to the Sponsor, as outlined in Section [5.4](#).

5.2.1 Adverse Events

According to the ICH guideline for Good Clinical Practice, an adverse event is any untoward medical occurrence in a clinical investigation subject administered a pharmaceutical product, regardless of causal attribution. An adverse event can therefore be any of the following:

- Any unfavorable and unintended sign (including an abnormal laboratory finding), symptom, or disease temporally associated with the use of a medicinal product, whether or not considered related to the medicinal product
- Any new disease or exacerbation of an existing disease (a worsening in the character, frequency, or severity of a known condition) (see Sections [5.3.5.9](#) and [5.3.5.10](#) for more information)
- Recurrence of an intermittent medical condition (e.g., headache) not present at baseline
- Any deterioration in a laboratory value or other clinical test (e.g., ECG, X-ray) that is associated with symptoms or leads to a change in study treatment or concomitant treatment or discontinuation from study drug
- Adverse events that are related to a protocol-mandated intervention, including those that occur prior to assignment of study treatment (e.g., screening invasive procedures such as biopsies)

5.2.2 Serious Adverse Events (Immediately Reportable to the Sponsor)

A serious adverse event is any adverse event that meets any of the following criteria:

- Is fatal (i.e., the adverse event actually causes or leads to death)
- Is life threatening (i.e., the adverse event, in the view of the investigator, places the patient at immediate risk of death)

This does not include any adverse event that, had it occurred in a more severe form or was allowed to continue, might have caused death.

- Requires or prolongs inpatient hospitalization (see Section 5.3.5.11)
- Results in persistent or significant disability/incapacity (i.e., the adverse event results in substantial disruption of the patient's ability to conduct normal life functions)
- Is a congenital anomaly/birth defect in a neonate/infant born to a mother exposed to study drug
- Is a significant medical event in the investigator's judgment (e.g., may jeopardize the patient or may require medical/surgical intervention to prevent one of the outcomes listed above)

The terms "severe" and "serious" are not synonymous. Severity refers to the intensity of an adverse event (e.g., rated as mild, moderate, or severe, or according to National Cancer Institute Common Terminology Criteria for Adverse Events [NCI CTCAE]; see Section 5.3.3); the event itself may be of relatively minor medical significance (such as severe headache without any further findings).

Severity and seriousness need to be independently assessed for each adverse event recorded on the eCRF.

Serious adverse events are required to be reported by the investigator to the Sponsor immediately (i.e., no more than 24 hours after learning of the event; see Section 5.4.2 for reporting instructions).

5.2.3 Adverse Events of Special Interest (Immediately Reportable to the Sponsor)

Adverse events of special interest are required to be reported by the investigator to the Sponsor immediately (i.e., no more than 24 hours after learning of the event; see Section 5.4.2 for reporting instructions). Adverse events of special interest for this study are as follows:

- Cases of potential drug-induced liver injury that include an elevated ALT or AST in combination with either an elevated bilirubin or clinical jaundice, as defined by Hy's Law (see Section 5.3.5.7)
- Suspected transmission of an infectious agent by the study drug, as defined below:

Any organism, virus, or infectious particle (e.g., prion protein transmitting transmissible spongiform encephalopathy), pathogenic or non-pathogenic, is considered an infectious agent. A transmission of an infectious agent may be suspected from clinical symptoms or laboratory findings that indicate an infection in a patient exposed to a medicinal product. This term applies only when a contamination of the study drug is suspected.

5.3 METHODS AND TIMING FOR CAPTURING AND ASSESSING SAFETY PARAMETERS

The investigator is responsible for ensuring that all adverse events (see Section 5.2.1 for definition) are recorded on the Adverse Event eCRF and reported to the Sponsor in accordance with instructions provided in this section and in Sections 5.4–5.6.

For each adverse event recorded on the Adverse Event eCRF, the investigator will make an assessment of seriousness (see Section 5.2.2 for seriousness criteria), severity (see Section 5.3.3), and causality (see Section 5.3.4).

5.3.1 Adverse Event Reporting Period

Investigators will seek information on adverse events at each patient contact. All adverse events, whether reported by the patient or noted by study personnel, will be recorded in the patient's medical record and on the Adverse Event eCRF.

After informed consent has been obtained but prior to initiation of study drug, only serious adverse events caused by a protocol-mandated intervention (e.g., invasive procedures such as biopsies, discontinuation of medications) should be reported (see Section 5.4.2 for instructions for reporting serious adverse events).

After initiation of study drug, all adverse events will be reported until 5 months after the final dose of study drug or until the patient receives his or her first dose in the OLE study (BN40955), at which time reporting will occur per the new study requirements. *For patients consented to version 6 of the protocol, who have discontinued study treatment and have entered the ETT schedule of assessments, AEs will be reported until 5 months after the last dose of study drug or until the EoT for ETT Week 101 visit (whichever is longer). For patients consented to version 6 of the protocol, who have received their last dose of study treatment less than 5 months before the scheduled Week 101 EoT for ETT visit, an additional safety telephone call should be performed 5 months after the last dose.*

Instructions for reporting adverse events that occur after the adverse event reporting period are provided in Section 5.6.

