- It has been clarified that all patients in the treatment period will discontinue study treatment and enter the early treatment termination (ETT) schedule. The previous version of the protocol already described the ETT schedule for following of individuals, for safety and efficacy outcomes, who have discontinued the study drug but not withdrawn consent for continued study participation (Sections 3.1.1, 4.2, and 4.6, and Figure 1 and 2). Additional clarification on visits and assessments required on the ETT schedule has been provided (Section 3.1.1.1, and Figure 3, and Appendices 1a and 1b).
- The ETT visit window has been extended from 28 (\pm 7 days) from last dose to within 56 days of the decision to discontinue study treatment (i.e., from 22 March 2021). This extension has been made to facilitate scheduling of the ETT visit using the existing planned visit schedule (Section 3.1.1.1, and Appendices 1a and 1b).

- It has been clarified that following the iDMC recommendation to discontinue study treatment dosing in this study, the Sponsor will be unblinded to treatment assignment, to allow for data analyses to occur, in order to enhance the understanding of RO7234292 effects and to inform RO7234292 program next steps (Sections 3.1.2, 4.2, and 4.5.9.22).
- End of study and length of study have been adjusted, as a result of all patients moving to the ETT schedule (Section 3.2).
- It has been clarified that patients should not perform any activity that is associated with a change in the ambient air pressure for at least 24 hours post lumbar procedure, irrespective if study treatment is administered or not (Section 4.5.5, Appendices 1a and 1b).
- As per protocol, individuals will have an LP at the ETT visit. Additional safety assessments including lumbar puncture and laboratory tests have been added to the end of treatment (EoT) assessment for ETT to ensure complete and adequate collection of follow-up safety outcomes (Section 4.5.5, Appendices 1a and 1b).
- Wording in Section 5.1.1 and Section 5.1.2 has been amended to be consistent with the latest available risk data as per the RO7234292 Investigator's Brochure Version 7.
- Adverse event reporting period has been clarified, as a result of all patients moving to ETT schedule and discontinuing study treatment (Sections 5.3.1 and 5.4.2.2).

TABLE OF CONTENTS

PROTOCOL AMENDMENT ACCEPTANCE FORM	14
PROTOCOL SYNOPSIS	15
1. BACKGROUND	28
1.1 Background on Huntington's Disease.....	28

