C-SSRS, neuroimaging assessments (neurologic safety sequences), and a review of any adverse events including related concomitant medications, as detailed in [Appendix 1a](#). Patients in Japan must be monitored in the hospital setting for at least 24 hours after Day 1 study drug administration. Discharge will be determined at the discretion of the principal investigator.

In the case of a failed IT bolus dosing procedure *or a failed CSF collection procedure* (e.g., due to an inadequate establishment of access to the IT space), a second attempt may occur up to 7 days after the originally scheduled attempt. For this additional visit, safety and tolerability evaluations on the day of LP administration will be performed as detailed in [Appendix 1a](#) and [Appendix 1b](#), including neurological examination (predose and postdose, *or pre-procedure if no study treatment is being administered*), vital signs, and a review of adverse events and concomitant medication. If the second attempt occurs more than 3 days after the first attempt, local laboratory analysis of coagulation factors (INR and/or PT, aPTT) and platelets need to be conducted again and results reviewed prior to the LP attempt (see [Appendix 1a](#)).

During the treatment period, a telephone safety follow-up call will be conducted for the months in which no clinic visits are scheduled to check for any change in patient status (i.e., adverse events, concomitant medications) since the patient's last visit (see [Appendix 1a](#)). Where deemed appropriate, an unscheduled clinic visit should be arranged for safety follow-up; no dosing will occur at these unscheduled visits. A safety follow-up telephone call will also be conducted approximately 2 months after the last in-clinic visit at Week 101.

Effective 22 March 2021, all patients will discontinue study treatment and will no longer be able to enter the OLE study (BN40955) after completing this study.

[figure not shown]
For patients enrolled in Study BN40423 who discontinue study treatment prematurely, but do not withdraw consent for continued participation in the study, an ETT schedule will apply (Section 3.1.1.1).

An iDMC and independent Data Coordinating Center (iDCC) will be employed to monitor and evaluate patient safety throughout the study as well as to evaluate evidence of early efficacy (see Section 3.1.2).

The Sponsor may choose to conduct one or more interim analyses during the study (further details are given in Section [6.12](#)).

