When applicable, study treatment administration will occur via a lumbar puncture using a needle inserted into the L3/L4 space, although placement at a different level (either in the space above or the space below) is allowed if patient anatomy or clinical judgment dictates. The left lateral position is mandatory in the first instance for the procedure for consistency of procedure practice across sites and within patients, unless patient-specific factors require use of the upright, sitting position or the physician/operator has pre-existing experience using LP/intrathecal bolus dosing in the sitting position and prefers the use of the upright sitting position, as guided by the patient, his or her judgment. Whichever position is used, once access is established to the IT space, the entire IT bolus procedure should be completed in the same position, to limit the risk of the needle losing position while the spinal needle is inserted. Subsequent LP administrations should occur using the same position.

Patients will be discouraged from resting supine after the lumbar puncture procedure and will be encouraged to mobilize immediately by walking around at a minimum and, if feasible, walking briskly for approximately 30 minutes, after which the postdose neurological examination can occur (*if study treatment was administered*). Patients should not perform any activity that is associated with a change in the ambient air pressure for at least 24 hours *post-LP procedure* (e.g., air travel, scuba diving, or hot air balloons).

Lumbar punctures will be performed as specified in the schedule of activities (see [Appendix 1](#)), with the last CSF sample obtained at the Week 101 end-of-treatment

visit. After discontinuation of study treatment, LPs will be performed at the ETT and EoT for ETT visits (see [Appendix 1a](#) and [Appendix 1b](#)). No study drug will be administered at these visits.

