5.1.1.1 Post-Lumbar Puncture Syndrome

RO7234292 is delivered directly to the CNS by IT lumbar puncture injection. Post-lumbar puncture syndrome (e.g., headaches, nausea, vomiting, infection, hemorrhage, nerve irritation pain) can occur with IT administration. Experience to date with post-lumbar puncture syndrome, as reported in the completed Phase I/IIa study, includes headache, which occurred after 10% of procedures and was transient and mild in the vast majority of patients.

In the recently completed Phase II OLE Study BN40697, post-LP syndrome events (such as post-LP syndrome, headache, migraine, nausea, vomiting or procedural headache) occurring within 5 days of LP were reported in 9 patients (39.1%) in the Q4W cohort and 13 patients (56.5%) in the Q8W cohort.

In Study BN40423 ODC, post-LP syndrome events (post-LP syndrome, headache, migraine, nausea, vomiting or procedural headache) occurring within 5 days of LP were

reported in 14 patients (38.9%) in the placebo cohort, 8 patients (22.9%) in the Q4W cohort and 14 patients (38.9%) in the Q8W cohort.

As 7 August 2020, in the ongoing Study BN40955, post-LP syndrome events (such as post-LP syndrome, headache, migraine, nausea, vomiting or procedural headache) occurring within 5 days of LP were reported in 7 patients (5.3%) in the Q8W cohort and 2 patients (2.7%) in the Q16W cohort.

The majority of these events were mild or moderate and non-serious. No events led to treatment interruption or discontinuation.

Patients should walk post-lumbar procedure (see Section 4.3.2.1). However, if a patient develops a headache after the lumbar puncture with characteristic features, which makes walking intolerable, the patient should be encouraged to first sit down and if the headache persists then *the patient should* lie in a comfortable position, which is most likely in the supine position owing to the postural nature of the symptoms. Supportive treatment may include rehydration, consumption of caffeinated drinks, simple analgesics, opioids, and antiemetics. If these conservative measures fail, more specific measures may be indicated.

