5.6 ADVERSE EVENTS THAT OCCUR AFTER THE ADVERSE EVENT REPORTING PERIOD

The Sponsor should be notified if the investigator becomes aware of any serious adverse event that occurs after the end of the adverse event reporting period (defined as greater than 5 months after the final dose of study drug), if the event is believed to be related to prior study drug treatment. These events should be reported through use of the Adverse Event eCRF. However, if the EDC system is not available, the investigator should report these events directly to the Sponsor or its designee, either by faxing or by

scanning and emailing the paper Clinical Trial Serious Adverse Event/Adverse Event of Special Interest Reporting Form using the fax number or email address provided to investigators.

5.7 EXPEDITED REPORTING TO HEALTH AUTHORITIES, INVESTIGATORS, INSTITUTIONAL REVIEW BOARDS, AND ETHICS COMMITTEES

The Sponsor will promptly evaluate all serious adverse events and adverse events of special interest against cumulative product experience to identify and expeditiously communicate possible new safety findings to investigators, IRBs, ECs, and applicable health authorities based on applicable legislation.

To determine reporting requirements for single adverse event cases, the Sponsor will assess the expectedness of these events using the following reference document:

- RO7234292 Investigator's Brochure

The Sponsor will compare the severity of each event and the cumulative event frequency reported for the study with the severity and frequency reported in the applicable reference document.

Reporting requirements will also be based on the investigator's assessment of causality and seriousness, with allowance for upgrading by the Sponsor as needed.

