^a All patients who discontinue study treatment prematurely but do not withdraw consent for continued participation in the study (this includes all patients from 22 March 2021) will attend a minimum of two and up to four in-clinic visits depending on which visits have already been completed at the time of study drug discontinuation (see [Figure 3](#)). Patients will complete an ETT visit within 56 days (8 weeks) of the decision to discontinue study treatment (i.e., 22 March 2021). Patients will also return to the clinic for FU study visits at Weeks 53 and 69 (if not already completed) for collection of clinical outcome data for the primary and secondary endpoints (see [Sections 2.1.1, 2.1.2, 2.2](#) and the table above). If the ETT visit falls within ± 30 days of either scheduled visits at Week 53 or Week 69, then only the ETT visit should be performed. Patients will also attend the scheduled EoT for ETT visit at Week 101. Study visits should be planned as per the study schedule, however under exceptional circumstances, a time window of ± 7 days can be utilized where shown.

Appendix 1b: Schedule of Activities for Early Treatment Termination (Applicable to all Patients from 22 March 2021) (cont.)

- ^b After study treatment discontinuation, a safety follow-up telephone call should be conducted every 8 weeks between the clinic visits. For patients consented to version 6 of the protocol who received their last dose of study treatment less than 5 months before the scheduled Week 101 EoT for ETT visit, an additional safety telephone call should be performed 5 months after the last dose. Telephone safety follow-up calls will assess any changes to ongoing adverse events or occurrence of new adverse events and changes to concomitant medication which should be documented in the eCRF. Unscheduled visits can occur based on the outcome of this safety follow-up call.
- ^c Excluding MRIs, which have a visit window of -14 to -7 days.
- ^d Vital signs include respiratory rate, pulse, temperature, and systolic and diastolic blood pressure while the patient is in a seated position after resting for approximately 5 minutes. All data should be recorded on the appropriate eCRF.

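### For patients last dosed 5 months or more before Week 101, adverse event reporting closes on the day of a protocol-mandated lumbar puncture, leaving later procedure-related events without a clear reporting route

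*Protocol*

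**What the plan says.** **The procedure.** The Version 6 summary of changes states that "Additional safety assessments including lumbar puncture and laboratory tests have been added to the end of treatment (EoT) assessment for ETT", in order to make follow-up safety data complete. Section 4.5.5 carries this into the current text: "After discontinuation of study treatment, LPs will be performed at the ETT and EoT for ETT visits". Appendix 1b schedules the LP accordingly, and no drug is given.

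**The reporting limit.** For ETT patients who consented to Version 6, Section 5.3.1 says "AEs will be reported until 5 months after the last dose of study drug or until the EoT for ETT Week 101 visit" and takes the longer of the two. Section 5.4.2.2 sets the same limit for serious events and events of special interest.

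**After the limit.** Section 5.6 asks for notice of a serious event only "if the event is believed to be related to prior study drug treatment". Appendix 1b footnote v adds deaths from any cause. Neither mentions events caused by a study procedure.

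**Contacts.** Under Appendix 1b footnote b, "a safety follow-up telephone call should be conducted every 8 weeks between the clinic visits". One further call, 5 months after the last dose, is for patients dosed less than 5 months before Week 101. Section 3.1.1 also says: "A safety follow-up telephone call will also be conducted approximately 2 months after the last in-clinic visit at Week 101". Appendix 1a footnote ee repeats that call, but Section 3.1.1.1 and Appendix 1b do not.

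**The concern.** The protocol's own definitions treat LP complications as reportable. Section 5.2.1 includes events related to a protocol-mandated intervention among adverse events. Section 5.1.1 names post-LP syndrome, spinal hematoma and meningitis as risks of the puncture, and Section 5.1.1.1 counts post-LP events over 5 days. Section 6.7 promises adverse event incidence by relationship to study drug or study procedure. A reporting period that ends on the day of the last puncture cannot cover those 5 days.

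There is also an unexplained asymmetry. Before the first dose, Sections 5.3.1 and 5.4.2.1 require reporting of serious events caused by a mandated intervention. After the last LP, Section 5.6 has no equivalent.

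At stake is complete safety capture for an invasive procedure that Version 6 added to improve safety follow-up. Complications of this last puncture would be under-recorded in some patients and not in others, depending on when they were last dosed.

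**Working it through.** The plan states no figure to reproduce. The check is date arithmetic on the injection visits, followed by a comparison of the contact rules.

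**Inputs**
- Injection visits, common to all three arms: Weeks 1 and 5, then every 8 weeks from Week 13 to Week 93, 13 in all (Table 1).
- Reporting ends at the later of last dose plus 5 months and the Week 101 visit (Sections 5.3.1 and 5.4.2.2).
- 5 months = 5 × 30.4375 = 152.2 days.
- Post-LP events are counted within 5 days (Section 5.1.1.1).

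**Formulas**
- Days from last dose at Week w to Week 101 = (101 − w) × 7.
- Reporting days left after the Week 101 LP = max(0, 152.2 − days to Week 101).

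| Last injection visit | Days to Week 101 | Reporting days after the LP |
|---|---|---|
| Weeks 1 to 69 | 700 to 224 | 0 |
| Week 77 | 168 | 0 |
| Week 85 | 112 | 40.2 |
| Week 93 | 56 | 96.2 |

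For 11 of the 13 possible last injection visits, no reporting time remains after the LP. The Week 77 result survives the visit windows: with both 7-day windows used to shorten the interval, 168 − 14 = 154 days, still above 152.2. For Weeks 85 and 93 the 5-day period is fully covered.

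**Calendar.** No dosing took place from 22 March 2021, so the latest possible last dose is 21 March 2021, and 5 months later is 21 August 2021. Any patient whose Week 101 visit falls after about that date is in the uncovered group. Enrolment dates are not given, so this cannot be turned into a patient count.

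**Contacts after Week 101**
- Calls every 8 weeks run between clinic visits, so none follows the last visit.
- The 5-month call excludes exactly the patients in the zero rows.
- The call about 2 months after Week 101 is in the general overview but not in the ETT sections. If made, it falls after reporting has closed for these patients.

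**A second inconsistency.** Section 5.6 and Appendix 1b footnote v still end the period at 5 months after the last dose, without the Week 101 extension. Read literally, that closes reporting before the Week 101 LP for the same patients, contrary to Sections 5.3.1 and 5.4.2.2.

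**The case against.** The best answer is that these patients are not out of contact. The Section 3.1.1 call is not restricted to patients who completed treatment, and the EoT for ETT visit is itself an in-clinic visit at Week 101. Sections 3.1.1, 4.5 and 4.6 send these patients to both Appendix 1a and Appendix 1b, and Appendix 1a has its own EoT for ETT column. Section 3.1.1.1 is headed a clarification of the existing design, so its silence need not cancel the call. Footnote ee says calls ask about new events, and Section 5.3.1 has investigators seek adverse events at every contact. This stands in part. A reader might infer that a site following the plan would make no contact after the last LP, and the documents do not establish that. They are ambiguous: Section 4.2 and Appendix 1a footnote b point to Appendix 1b for the ETT schedule, and Appendix 1b omits the call. The call also does not reopen a period that has closed.

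Other points also stand. Events on the day of the LP are captured, and Section 5.5.1 requires follow-up of each to resolution or stability. Some later serious events may still qualify under Section 5.6. Section 5.1.2.2 describes chemical and aseptic meningitis among drug-related concerns, and Table 5 makes relatedness the default. Deaths and local reporting duties remain. What is left is non-serious post-LP events, and serious ones firmly attributed to the puncture, that begin after the visit.

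A reader might also estimate a number of lost events from Section 5.1.1.1, which reports "headache, which occurred after 10% of procedures". The documents do not support such a count. The affected share of the approximately 801 planned patients is unknown. The rate comes from Phase I/IIa procedures that included an injection, and some headaches would start the same day. The same section gives 5.3% and 2.7% of patients with post-LP events within 5 days in Study BN40955, on a per-patient basis that is not interchangeable with a per-procedure rate.

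**Conclusion.** The gap is real and limited. It affects ETT patients whose last scheduled dose was at Week 77 or earlier, and only LP complications that start after the Week 101 visit and are attributed to the procedure. For them the stated limit leaves no reporting days after the LP, against the 5 days over which the protocol itself counts post-LP events. The post-Week-101 call does not clearly close the gap, and the passages on it must be reconciled.

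The conclusion rests on taking 5 months as about 152 days, on visits within their windows, and on the longer reporting limit of Sections 5.3.1 and 5.4.2.2. The shorter wording in Section 5.6 and Appendix 1b would make the gap wider.

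Uneven capture should not be read as bias between arms. The limit depends on time since last injection, all arms share the same injection visits, and dosing stopped for everyone on one date. No efficacy analysis is touched. This is a point that should be fixed, not one that undermines the trial.

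**What to change.** 1. In Sections 5.3.1, 5.4.2.2 and 5.6 and Appendix 1b footnote v, end adverse event and serious adverse event reporting for ETT patients at a contact after the Week 101 LP, and use the same limit in all four places. Keep the later limit for patients whose 5-month period runs beyond that contact.
2. In Section 3.1.1.1 and Appendix 1b, state that the post-Week-101 call already described in Section 3.1.1 and Appendix 1a footnote ee applies to all ETT patients.
3. In Section 5.6, widen the criterion to serious events believed related to prior study drug treatment or a study procedure.

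The cost is wording in five places and one telephone call per affected patient, which Section 3.1.1 already describes. If that call becomes the closing contact, safety data collection for the last patients runs about 2 months past Week 101, and the timing statement in Section 3.2 should be checked against it.
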